4.1.4. Benchmarking equipment for AD plasma biomarkers

2D-BioPAD plasma biomarker values measured in both the retrospective and prospective studies will be compared with the same plasma biomarkers (e.g., Quanterix Simoa-based) measured at the UEF Brain Research Unit biomarker laboratory¹⁷. The UEF Brain Research Unit laboratory offers diagnostic services of AD biomarkers available for physicians and hospitals since 2005 and has extensive experience with large-scale international studies on AD fluid biomarkers. Quality management system is based on international standards for quality management and for clinical laboratories¹⁸. The laboratory has ISO 15189 accreditation (FINAS

¹⁷ <https://sites.uef.fi/aivobiomarkkeritutkimukset/?lang=en>

¹⁸ <https://sites.uef.fi/aivobiomarkkeritutkimukset/>

Finnish Accreditation Service) for CSF β -amyloid 42, t-tau and p-tau analyses, which are run using automated immunoassays (Roche Elecsys).

In the EU, AD plasma biomarkers are not currently available in clinical practice on a wide scale. Finland is one of the few EU countries with available diagnostic services of AD plasma biomarkers for clinical practice, i.e., Quanterix Simoa-based plasma NfL service offered by the UEF Brain Research Unit biomarker laboratory (other Simoa-based AD plasma markers will soon become available). These in vitro diagnostic medical devices of the UEF laboratory are registered with the Finnish Medicines Agency (FIMEA, e.g.¹⁹). Other devices, reagents etc used for diagnostic services by the laboratory are CE-marked.

Depending on availability / validation status, Fujirebio Lumipulse-based plasma AD biomarkers may be considered as an alternative for benchmarking. Simoa- and Lumipulse-based plasma markers have been shown to have similar diagnostic accuracy in research studies, e.g.^{20 21}.

4.1.4.1. *State-of-the-art CSF biomarkers*

Standard assessment procedures at all three clinical study centres include CSF biomarkers measured using state-of-the-art equipment: Roche Elecsys (β -amyloid 42, t-tau and p-tau181) at UEF and GAADR, or Fujirebio Lumipulse (β -amyloid 42/40, t-tau and p-tau181) at GAADR and ZI. As lumbar puncture is an invasive procedure, CSF biomarkers are measured based on clinical indication and/or patient consent, provided that no contraindications are present. CSF biomarker information is used together with other clinical, cognitive, neuroimaging etc information to establish the diagnosis in standard clinical practice.

To reduce patient burden, the 2D-BioPAD clinical pilot study will use CSF biomarker values measured during standard assessment procedures at the clinical study centres. For the retrospective study, existing plasma samples will be selected from individuals who also have available CSF biomarker data. Each assay has established cut-offs for AD pathology which are used in clinical practice. The Lumipulse and Elecsys CSF AD assays have been shown to have high analytical and clinical performances²², with strong correlation and high concordance in identifying AD pathology²³.

4.1.5. *Ethical and regulatory aspects*

4.1.5.1. *Ethical aspects*

The investigators at all study centres will ensure that this study is conducted in conformance with the principles of the “World Medical Association Declaration of Helsinki” (52nd WMA General Assembly, Edinburgh, Scotland, October 2000; including the Notes of Clarification as added in 2002, Washington; 2004, Tokyo; 2008, Seoul; and 2013, Fortaleza), International Conference on Harmonisation (ICH) guidelines for Good Clinical Practice (GCP), and relevant legislation in each participating country.

Ethics Committee review

¹⁹<https://sites.uef.fi/aivobiomarkkeritutkimukset/wp-content/uploads/sites/112/2023/08/Vakuutus-Biomarkkerilaboratorio-140823.pdf>

²⁰ Pilotto A., et al. Plasma p-tau217 in Alzheimer's disease: Lumipulse and ALZpath SIMOA head-to-head comparison. medRxiv [Preprint]. 2024 May 3:2024.05.02.24306780. doi: 10.1101/2024.05.02.24306780

²¹ Dakterzada, F., et al. Assessment of the Correlation and Diagnostic Accuracy between Cerebrospinal Fluid and Plasma Alzheimer's Disease Biomarkers: A Comparison of the Lumipulse and Simoa Platforms. *Int. J. Mol. Sci.* 2024, 25, 4594. <https://doi.org/10.3390/ijms25094594>

²² Dakterzada F, et al. Assessment of the Concordance and Diagnostic Accuracy Between Elecsys and Lumipulse Fully Automated Platforms and Innostest. *Front Aging Neurosci.* 2021 Mar 4;13:604119. doi: 10.3389/fnagi.2021.604119

²³ Campbell MR, et al. P-tau/A β 42 and A β 42/40 ratios in CSF are equally predictive of amyloid PET status. *Alzheimers Dement (Amst).* 2021 May 18;13(1):e12190. doi: 10.1002/dad2.12190

The relevant clinical pilot study documents have been submitted to the following Ethics Committees as per standard local procedures:

- Regional Medical Research Ethics Committee of the Wellbeing Services County of North Savo (UEF study center, Finland)
Status: approved September 17, 2024
- Bioethics Committee of Alzheimer Hellas (GAARDR study centre, Greece)
Status: approved September 11, 2024
- Ethics Committee (ZI study center, Germany)
Status: in processing

Approval by the relevant Ethics Committee must be obtained before starting the study at each centre and will be documented in a letter to the study centre investigator, specifying the date of approval, the composition of the ethics committee, and version and date of submitted documents.

Any substantial change and/or amendments to the study protocol will be submitted to the relevant Ethics Committees in accordance with current requirements. Approval by the Ethics Committee must be obtained before the implementation of any substantial change or amendment, except for changes necessary to remove any apparent immediate hazard to the participant.

Informed consent

Prior to study enrolment, written informed consent will be obtained from each participant (patients and HCPs). It is the responsibility of the study centre investigator to make sure written informed consent is obtained after adequate explanation of the aims, methods, source of funding, the anticipated benefits and potential risks of the study and the discomfort it may entail. The nature, significance and scope of the study will be explained in writing and verbally in an appropriate and comprehensible manner. Care should be taken to ensure that sufficient time is allowed for the decision-making process. It will be made clear that participants may withdraw their consent to participate in the study at any time without giving reasons. The original informed consent forms (ICFs) will be kept in a study folder at each study centre and stored separately from the study data. A copy of the written study information and the ICF will be handed out to the participant.

In the case of patients who are diagnosed with AD or other dementia, ability to provide written informed consent for the study will be established according to the already existing standard procedures at each study centre. Individuals with impaired capacity to consent will not be eligible for the study. Each clinical study centre will adhere to the relevant local/national regulations and ethical guidelines to determine when an informant/legally acceptable representative is necessary and to ensure that the consent process is conducted appropriately.

Disclosure of AD blood biomarker results

Given that the overall aim of this clinical pilot study is to evaluate and validate AD blood biomarkers measured using the 2D-BioPAD diagnostic aid, these biomarker results will not be disclosed to patients and will not be used by HCPs for making diagnosis and treatment/care decisions. AD blood biomarker results measured using state-of-the-art equipment may be disclosed to patients and may be used by HCPs for making diagnosis and treatment/care decisions only if they are already included in the centre-specific standard assessment procedures. In such cases the disclosure and related procedures will be conducted by the treating physician at the relevant study centre, i.e., not as part of the 2D-BioPAD clinical pilot study.

Data protection and confidentiality of study data

All investigators, study staff and other parties involved in the study must comply with the requirements of the General Data Protection Regulation (GDPR) and relevant national data protection legislation as applicable regarding the collection, storage, processing, and disclosure of personal information.

All team members, partners, and collaborators who have access to the data and are involved in the study are responsible for treating subject and study information as confidential. The investigators will ensure that the subject information will not be made publicly available. To maintain subjects' confidentiality, study records and samples will be de-identified. All participants will be given a random subject ID and all data and samples will be processed, analysed, saved, and stored as de-identified. Identification code keys linking the subjects' names and other personal information to the subjects' identification number must be stored in the Investigator Site File, in a locked or password protected location at each centre separately from all other data. Access to the code keys and subjects' personal information will be given only to the main investigators or those research-team members for whom access is necessary to conduct the study.

Sharing of de-identified data and samples between Consortium partners will be done using secure encrypted methods after a material transfer agreement has been signed by all relevant partners.

Data and samples storage and archiving

All clinical pilot study data in paper format, as well as samples collected, will be stored as de-identified in a locked location at each study centre. De-identified data will be also saved for the study duration in an electronic format in the centre institution disk/server space which will be protected with username and password. Access right will be limited, and granted, only to the members of the research group at the respective centre. All participating institutions have information protection and processing policies and the relevant IT infrastructure for their implementation.

Participant's personal information, such as name, social security number, and contact information, will be stored and kept separately from all other data and samples, in a password-protected disk/server space and/or locked location with limited access rights at each study centre. Access to the code keys and subjects' personal information will be granted only to those researchers at the respective study centre for whom access is absolutely necessary in order to conduct the study.

De-identified data and samples will be shared between 2D-BioPAD Consortium partners for analyses as specified in the protocol. Prior to the sharing of data and samples, a material transfer agreement will be prepared, approved, and signed by all partners involved. Any excess of samples shipped outside of the study centre where samples were collected will be destroyed after completion of the analysis.

After the end of the study, research data in paper format and electronic de-identified data from each study centre will be archived at the respective study centre according to the relevant local/national regulations.

Insurance/Compensation

The study participants will be insured according to the relevant legislation at each study centre. No financial compensation will be provided to research participants for participating in the study.

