Lumbar puncture is not done in all patients, due to contraindications, refusal of some patients to consent to an invasive and burdensome procedure, or guidelines not recommending CSF biomarkers in specific cases (e.g. no objective cognitive impairment and no other dementia risk indicators). State-of-the-art CSF biomarkers are estimated to be available via routine assessments in about 100-150 of the total 300 patients in the prospective study. Plasma biomarkers using benchmarking equipment (section 4.1.4 Benchmarking equipment for AD plasma biomarkers) will thus be measured in all 300 patients. For the retrospective study, existing plasma samples will be selected if CSF biomarker data is also available from routine assessments. Aspects related to

CSF biomarker assays used at each study centre are detailed below in section 4.1.4.1 State-of-the-art CSF biomarkers.

Blood

- Blood sampling procedures, i.e. routine sampling from all patients versus selected groups, sample storage for research purposes
- Current availability of AD blood biomarkers for routine clinical use
- Availability of kidney and liver function measurements, including list of relevant biomarkers

AD blood biomarkers are not currently available for routine clinical use at the study centres, except for plasma NFL in Finland provided by the UEF biomarker laboratory. Blood sampling is common at all study centres, especially as part of research studies. Kidney and liver function measurements are available either measured at the study centre or at primary care; creatinine and ASAT are common across all study centres.

A set of conditions for storage of existing samples applicable across study centres was identified (Table 4).

Neuroimaging

- Structural MRI procedures, i.e. routine for all patients versus selected groups
- Possibility to retrieve MRI-related data for research
- Availability and type of PET scans, and procedures (routine for all patients versus selected groups)

Structural brain MRI is done at all study centres, except in patients with MRI contraindications. Quantitative image analysis is not done as part of routine procedures but validated semi-quantitative visual rating scales (e.g. for hippocampus atrophy and white matter lesions) are used at all centres. PET scans (e.g. FDG-PET, amyloid-PET) are only done in selected cases due to higher cost.

B) Other assessments done as part of research

- Cognitive tests
- Daily life functioning level
- Other

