4.4.2. Prospective study outcomes

Table 9. Overview of the prospective study outcomes

Outcome type	Description
Primary	
 Sensitivity, specificity, positive and negative predictive values of plasma biomarkers measured with the 2D-BioPAD prototype versus benchmarking equipment (same as above) for identifying AD diagnosis established as per centre-specific standard procedures. Overall experience of HCPs with the 2D-BioPAD diagnostic aid Overall experience of patients with the 2D-BioPAD diagnostic aid
Secondary	
 Comparison of plasma biomarker values between 2D-BioPAD prototype and benchmarking equipment, considering the potential impact of other parameters, e.g., demographics, comorbidities, disease stage Sensitivity, specificity, positive and negative predictive values of plasma biomarkers measured with the 2D-BioPAD prototype for identifying AD-related pathology (e.g., β-amyloid, tau), as indicated by either plasma biomarkers from benchmarking equipment or, where available, CSF biomarkers measured during routine assessments at the clinical study centres using state-of-the-art equipment. Investigating plasma biomarkers measured with 2D-BioPAD prototype versus benchmarking equipment in relation to cognitive, clinical and other data Assess if user experience (HCPs and patients) with the 2D-BioPAD diagnostic aid varies by country, clinical specialty, and/or years of experience Assess if the information provided to HCPs via the digital interface of the 2D-BioPAD diagnostic aid is understandable and relevant Collect feedback for diagnostic aid improvement from HCPs and patients

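### Routine plasma NfL may inform the reference diagnosis at the Finnish centre, so NfL accuracy is exposed to incorporation bias there, and Table 6 would not show which patients are affected

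*Protocol*

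**What the plan says.** Protocol section 4.4.2 (Table 9) makes the first primary prospective outcome the set of accuracy measures (sensitivity, specificity and both predictive values) for "plasma biomarkers measured with the 2D-BioPAD prototype versus benchmarking equipment (same as above) for identifying AD diagnosis established as per centre-specific standard procedures". Section 4.4.3 states the main hypothesis as noninferiority of device accuracy to benchmark accuracy, and compares AUCs marker by marker.

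Section 4.1.5.1 (disclosure of AD blood biomarker results) keeps device results out of diagnosis and care. For other plasma results it says that "AD blood biomarker results measured using state-of-the-art equipment may be disclosed to patients and may be used by HCPs for making diagnosis" and for care decisions, but "only if they are already included in the centre-specific standard assessment procedures".

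Section 4.1.3 (Blood) describes current availability: "AD blood biomarkers are not currently available for routine clinical use at the study centres, except for plasma NFL in Finland provided by the UEF". Section 4.1.4 says this NfL service is Simoa-based and adds that "other Simoa-based AD plasma markers will soon become available". The same section says that device values "will be compared with the same plasma biomarkers (e.g., Quanterix Simoa-based) measured at the UEF Brain Research Unit biomarker laboratory". Lumipulse is kept open as an alternative benchmark. NfL is in the benchmark panel in Table 6.

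**The concern.** If a plasma result helps to make the diagnosis, the accuracy of that marker against the diagnosis is partly circular. Here the rule is asymmetric. A routine result from the benchmark's platform and laboratory may enter the diagnosis at one centre, while the device result may enter it nowhere.

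Two things are at stake for the affected marker. First, both assays look more accurate than they would against a diagnosis made without the marker, because both measure the same analyte. Sensitivity, specificity and predictive values are themselves primary outcomes and will inform later confirmatory studies. Second, the contrast between the assays can tilt toward the benchmark, against the noninferiority hypothesis, and the effect could pass for a real difference between centres.

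The practical gap is in data collection. Table 6 records routine CSF, APOE, amyloid-PET and FDG-PET results where available. It has no entry for a routine plasma AD result, nor for whether one was known at diagnosis. A later analysis cannot separate patients on an item that was never collected.

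**Working it through.** **Can it happen, and where?**

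1. Permission: yes, if the marker is part of the centre's standard assessment (4.1.5.1).
2. Marker and centre: NfL in Finland only, as the protocol stands (4.1.3).
3. Same platform and laboratory as the benchmark: yes, if Simoa is kept (4.1.4).
4. Blinding: the restriction on healthcare professionals in 4.3.2 stands in a paragraph about device results. It does not address routine plasma results.
5. Timing: the study visit follows the diagnosis (4.3.2). What could enter the baseline diagnosis is therefore an earlier routine NfL result, not the study's benchmark value. Patients with an inconclusive diagnosis can be re-diagnosed up to one year later (4.3.3.2, 4.3.4.3), and a routine result could enter then too.

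**Share of patients.** The sample size of 300 rests on precedent, so there is no power figure to reproduce. Its parts add up: 30 + 270 = 300 and 3 × 100 = 300. The Finnish share is about 100/300, or one third.

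**Size under an assumed model.** No input below comes from the protocol.

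- 1.5 million simulated subjects, half diseased, one third at the exposed centre.
- Analyte: separation of 0.7 or 1.4 SD between groups, biological SD 1.
- Benchmark = analyte + error (SD 0.3). Device = analyte + independent error (SD 0.3 or 0.6).
- Earlier routine result = benchmark value + extra error (SD 0.15).
- Work-up score C: separation 2 SD. Without NfL, the diagnosis is positive if C > 1.
- With NfL, it is positive if (C − 1) + w × (routine result − half the separation) > 0, with w = 0.5 or 1.0, in 50% or 100% of patients at the exposed centre.

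Results with equal assay error (SD 0.3 for both), as AUC for benchmark / device:

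| Separation | w, share using NfL | Pooled | Pooled gap | Finland | Finland gap |
|---|---|---|---|---|---|
| 0.7 | none | 0.624 / 0.624 | 0.000 | 0.624 / 0.625 | +0.001 |
| 0.7 | 0.5, 50% | 0.645 / 0.643 | −0.002 | 0.686 / 0.681 | −0.005 |
| 0.7 | 1.0, 100% | 0.693 / 0.687 | −0.006 | 0.830 / 0.812 | −0.018 |
| 1.4 | none | 0.724 / 0.724 | 0.000 | 0.724 / 0.724 | 0.000 |
| 1.4 | 0.5, 50% | 0.744 / 0.743 | −0.001 | 0.783 / 0.779 | −0.004 |
| 1.4 | 1.0, 100% | 0.782 / 0.777 | −0.004 | 0.897 / 0.884 | −0.013 |

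The pooled rise for the benchmark runs from 0.744 − 0.724 = 0.020 to 0.693 − 0.624 = 0.069. For the device it runs from 0.743 − 0.724 = 0.019 to 0.687 − 0.624 = 0.063.

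With a noisier device (error SD 0.6), a real pooled deficit of 0.012 to 0.018 becomes 0.016 to 0.027.

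Two limits of the model matter:

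- The tilt arises because the routine result carries the benchmark's own assay error. If assay error differed wholly from run to run, two assays of equal error would rise together and the tilt would vanish.
- The rise is measured against the same model without NfL, where an imperfect work-up already lowers AUC. It is a shift in apparent AUC, not a measured distance from the truth.

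**The case against.** The strongest objection is that the protocol says NfL is available in Finland, not that it is part of the Finnish work-up. Section 4.1.4.1 describes the diagnosis as resting on CSF together with clinical, cognitive and imaging information, and does not name plasma. This stands: the plan is exposed to the bias, and the documents do not show that it is present.

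A reader might infer that every plasma marker is affected. The documents do not support this. Markers are compared one at a time, and only NfL is routine now. The remark that other Simoa markers are coming gives no date and does not say that they will join any centre's standard assessment.

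A reader might also infer that the benchmark is scored against itself. That is too strong, because the study sample follows the baseline diagnosis and Lumipulse may replace Simoa. Nor does the protocol say that centres will be analysed only in pooled form.

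A larger size is tempting too. Suppose the diagnosis follows the benchmark call in a share q of Finnish patients. The apparent accuracy gap there is then q × (1 − agreement between assays). With independent errors at 0.85 accuracy, agreement is 0.85² + 0.15² = 0.745, so q = 10% to 50% gives 2.55 to 12.75 points, or 0.85 to 4.25 pooled. But two assays of one analyte in one patient should agree far more often. At an assumed agreement of 0.90 the Finnish gap is 1.0 to 5.0 points (0.3 to 1.7 pooled); at 0.95 it is 0.5 to 2.5 (0.2 to 0.8 pooled). Nothing in the protocol suggests a diagnosis that follows NfL alone in up to half of patients.

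It is also fair that device and benchmark are compared against CSF status, which contains no plasma result. That gives a partial check, but CSF is expected in only about 100 to 150 of 300 patients, and in the prospective stage CSF-defined pathology is a secondary outcome. Finally, the CRFs are still to be designed (due M24). That makes the change easy; it does not make it unnecessary.

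**Conclusion.** The concern holds in limited form. The protocol permits a routine plasma result to shape the reference diagnosis while barring the device result. As written, this can concern only Simoa NfL at the Finnish centre, and so only NfL accuracy and combinations that include NfL. Other markers would be exposed if they entered a centre's routine use during the prospective stage (M30 to M48), including before a follow-up diagnosis.

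The size is unknown, because use and weight of NfL are not stated. Under the shared-analyte model with equal assay error, the spurious device deficit is about 0.001 to 0.006 in pooled AUC and 0.004 to 0.018 within Finland. The larger effect is on absolute performance: the apparent pooled AUC of both assays may be inflated by about 0.02 to 0.07. These figures rest wholly on the assumed inputs and show direction and order of size only. The case for acting is that the exposure is cheap to record now and could not be identified later from Table 6 as it stands.

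**What to change.** Add one item to Table 6 and the CRF: which plasma AD markers, if any, were known to the diagnosing team before the baseline or follow-up diagnosis was fixed, with the date.

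In 4.4.3, keep the all-patient comparison as primary. For each affected marker, add a sensitivity analysis restricted to patients diagnosed without that marker, and show results by centre. The restricted set should not become primary: if NfL is ordered selectively, restriction changes the case mix and gives each marker a different population.

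The cost is one CRF field, a sentence in 4.4.3 and a less precise sensitivity estimate, since up to about 100 Finnish patients could drop out of it for NfL. Routine care is unchanged. If the Finnish centre does not use NfL in diagnosis, the field will show that and the question closes.
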